#### Simultaneity Judgement Training (SJT)

Differs from SJ in that participants receive feedback ("Correct!" or "Incorrect") after each response. SOA is initially set at 350 ms for ease and reduced after 3 correct responses or

increased after 1 error using a 40 ms staircase protocol. Each SOA is tested 30 times. Three blocks are administered with optional rest between them. Participants repeat SJ task before and after training.

#### Rubber Hand Illusion Protocol

Participants undergo classic Rubber Hand Illusion protocol with visuotactile stimulation. Tactile stimulation (via brush) varies in frequency and is applied to the dorsum of the participant's hand. Participants rate pleasantness using a 100-point visual analog scale. They then observe a rubber hand being touched synchronously or asynchronously with their hidden hand. The illusion is rated using a 100-point visual analog scale.

### **4. Statistical Analysis**

To confirm the study hypotheses, statistical analysis will be conducted in the following steps:

Pearson's correlation will be used to assess associations between formal characteristics of ritualized actions (J-Watcher scores), OCD symptom severity (Y-BOCS), childhood-adolescent trauma (CTQ), affectivity (HAM-D), pre-psychotic basic symptoms (FBF and SPI-A), personality traits (SCID-5-PD), temperament traits (TCI, ATQ), and functioning (SOFAS).

To evaluate the factors affecting overall functioning, in the case of significant correlations among the aforementioned variables, linear regression analyses (Enter Method) will be conducted, using SOFAS total score as the dependent variable and demographic variables and questionnaire scores as independent variables. The same analysis will be applied to assess variables involved in insight loss, using the total BABS score as the dependent variable.

Simultaneity Judgement will allow estimation of individual audio-tactile simultaneity ranges (SR). To obtain SR values, the percentage of simultaneous responses across all SOAs for each participant will be calculated. An Independent Channels Model will be fitted to each participant's response distribution. Unlike typical psychometric models (e.g., Gaussian, Logistic), ICM is generative and models underlying sensory and decisional processes.

This procedure will be conducted individually for each participant and stimulus combination. Data from individuals whose responses do not fit the ICM model significantly ( $p < 0.05$ ) will be excluded from further analysis. SR values from both experimental groups will then be compared and correlated with psychopathological scales using standard parametric (or non-parametric if data are non-normally distributed) tests.

For each participant, for each SOA, the median value will be calculated for the SR task pre- and post-training. This will determine how often participants correctly judged stimulus simultaneity and whether training improved accuracy. Median values from both groups will then be compared and related to psychopathological scale results.

Additionally, participants will undergo the Rubber Hand Illusion protocol with visuotactile stimulation. The resulting data will also be analyzed in relation to psychopathological variables using standard parametric (or non-parametric, if applicable) statistical tests.

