## **2. Rationale and Study Hypotheses**

The primary objective of this study is to conduct a comprehensive investigation of the psychopathology of the Obsessive-Compulsive Spectrum, exploring not only the content characteristics of obsessive-compulsive symptoms, but also the formal modalities of expression—particularly the structure of the compulsive ritual—and how these aspects may affect the individual's global functioning.

Additionally, the study aims to assess possible predisposing factors to loss of insight in OCD, particularly the potential etiopathogenetic role of trauma, personality traits, affective factors, or OCD severity, with the goal of identifying subgroups of patients who may be more responsive to therapy.

Furthermore, it seeks to evaluate how patients with OCS and schizophrenia-spectrum symptoms respond to multisensory stimuli (auditory, tactile, and audio-tactile), in order to identify correlations between their capacity for audiovisual-tactile integration and psychopathological variables—especially trauma—and the structure of the ritual. A deficit in the ability to integrate signals at the cortical level could lead to unreliable perceptions, which may be a core feature of the illness, from which obsessive phenomena such as the need for checking and repetition emerge.

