#### *3.2 Inclusion and Exclusion Criteria*

*3.2a Inclusion Criteria:* A. Diagnosis of OCD and/or Schizophrenia Spectrum Disorder according to DSM-5, as defined by a structured interview (SCID-5-CV). B. Age between 18 and 65 years. C. Patient agreement to participate in the study.

*3.2b Exclusion Criteria:* A. General medical condition that could be related to the mental disorder. B. Alcohol or substance dependence or abuse. C. Cognitive deterioration (score below 25 on the Mini Mental State Examination).

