#### *3.3 Procedure*

All patients enrolled in the study will complete the following questionnaires:

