##### *3.3a Clinical and Demographic Variables*

Participants will complete a questionnaire including age, sex, years of education, family status, employment status, and housing situation. Through an initial brief interview and data retrieved from clinical records, information will be extracted on diagnosis at onset, initial treatment, family history, age at onset, and current therapy. A clinician-rated scale evaluating patient functioning (SOFAS) will also be completed. Lastly, the number of monthly visits to the relevant service will be recorded.

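### The correlations and the SOFAS and BABS regressions name neither a diagnosis term nor a restriction to OCD, although both diagnoses are enrolled and the insight question concerns OCD

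*Protocol*

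**What the plan says.** Eligibility (Protocol section 3.2a) is "Diagnosis of OCD and/or Schizophrenia Spectrum Disorder according to DSM-5", established by structured interview at entry. Section 3.3 states: "All patients enrolled in the study will complete the following questionnaires".

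Section 4 then sets out:

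- **Correlations.** Pearson's "correlation will be used to assess associations between formal characteristics of ritualized actions", Y-BOCS, CTQ, HAM-D, FBF, SPI-A, SCID-5-PD, TCI, ATQ and SOFAS.
- **Functioning model.** Where correlations are significant, an Enter-method linear regression "using SOFAS total score as the dependent variable and demographic variables and questionnaire scores as independent variables".
- **Insight model.** "The same analysis will be applied to assess variables involved in insight loss, using the total BABS score as the dependent variable".
- **Simultaneity range (SR).** "SR values from both experimental groups will then be compared and correlated with psychopathological scales". The groups are not defined. The pre/post-training medians are also compared between two groups.

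The demographic items in section 3.3a are "age, sex, years of education, family status, employment status, and housing situation". Diagnosis at onset is recorded separately from interview and records, and section 4 does not name it as a predictor. Section 2 states the insight aim: "the study aims to assess possible predisposing factors to loss of insight in OCD".

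**The concern.** Two things do not fit together.

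First, the insight question is about OCD, but the BABS regression is not limited to patients with OCD. Section 3.3c describes BABS as transdiagnostic, so patients with only a schizophrenia-spectrum disorder will have scores and, as written, can enter the model.

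Second, the named predictor classes leave diagnosis out of analyses that, on a plain reading, use everyone. The protocol gives reasons to expect some differences between the diagnoses. Y-BOCS measures OCD severity. SPI-A was designed for people at risk of schizophrenia. Section 1.1b notes that some authors place poor-insight OCD in the schizophrenia spectrum.

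Where both variables of a pair differ by diagnosis, a pooled association can arise with no link inside either diagnosis. A factor reported as bearing on insight loss in OCD might then only separate the two diagnoses. If the differences run in opposite directions, a real within-diagnosis association can be cancelled. Because section 4 makes the regressions depend on significant correlations, such an artefact can also decide which regressions are run.

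**Working it through.** The protocol states no sample size, alpha, power, effect size or diagnosis mix, so it has no figure to reproduce. All values of n, p and d below are assumptions.

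**Setup.** p is the share of one diagnosis, q = p(1−p), and d1 and d2 are the differences between diagnoses in within-diagnosis SDs. With within-diagnosis correlation r_w:

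pooled r = (r_w + q·d1·d2) / √[(1 + q·d1²)(1 + q·d2²)]

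**1. Spurious association (r_w = 0, d1 = d2 = d, n = 100).** Pooled r is then q·d²/(1 + q·d²). The rejection rates are simulated, 4,000 runs per cell, two-sided 0.05.

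| Mix | d | Pooled r | Chance of p<0.05 |
|---|---|---|---|
| 50:50 | 0.3 | 0.0225/1.0225 = 0.02 | 5.5% |
| 50:50 | 0.5 | 0.0625/1.0625 = 0.06 | 9% |
| 50:50 | 0.8 | 0.16/1.16 = 0.14 | 29% |
| 50:50 | 1.0 | 0.25/1.25 = 0.20 | 54% |
| 50:50 | 1.5 | 0.5625/1.5625 = 0.36 | 97% |
| 20:80 | 1.0 | 0.16/1.16 = 0.14 | 27% |

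Fisher's z agrees. At d = 1, atanh(0.20)·√97 = 2.00, which gives 51%. At d = 1.5, atanh(0.36)·√97 = 3.71, which gives 96%.

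Other sample sizes at d = 1: with a 50:50 mix, 33% at n = 60 and 83% at n = 200; with a 20:80 mix, 19% and 50%.

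**2. After adjustment.** When diagnosis means are removed from both variables, the rate is 4.4% to 5.8% in every scenario run (p = 0.2, 0.3, 0.5; d = 0.3 to 1.5; n = 60, 100, 200).

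**3. Multivariable regression.** BABS is not in the Pearson list; it appears only as a regression outcome. Suppose k predictors and the outcome are all shifted by d and unrelated within diagnosis. Each pooled coefficient is c = q·d²/(1 + k·q·d²). The residual variance is 1 + c, and the diagonal of the inverse predictor covariance is 1 − c. The expected t value is therefore about c·√[(n − k − 1)/(1 − c²)]. With a 50:50 mix, d = 1 and n = 100:

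- k = 6: c = 0.25/2.5 = 0.100; t = 0.100·√(93/0.990) = 0.97; about 16% per predictor.
- k = 10: c = 0.25/3.5 = 0.0714; t = 0.0714·√(89/0.995) = 0.68; about 10% per predictor.

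The rate falls because the shifted scores together stand in for diagnosis, but it stays above 5%.

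**4. Masking.** With a true r_w of 0.25, a 50:50 mix, d1 = +1 and d2 = −1, pooled r = (0.25 − 0.25)/1.25 = 0.

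**The case against.** **Pooling is inferred.** Section 4 never says that these analyses use all patients. The ritual, insight and trauma aims are framed around OCD, and an analysis set may be left to a statistical analysis plan, which was not available here. This stands as a limit on wording. It does not answer the point, because the protocol itself fixes the model type and predictor classes, and an analyst following it would leave diagnosis out.

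**Large differences are not shown.** Section 1.2 presents basic symptoms as a possible bridge between OCD and psychosis, and section 1.1c treats childhood trauma as a risk factor common to several disorders. Neither implies a large gap on FBF, SPI-A or CTQ. This stands: a reader might infer that false links will appear, but the documents support only that they can. At d of 0.3 or less the effect is negligible.

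**The single-correlation rates do not describe the insight model.** This stands. A reader might carry the 51–97% figures over to BABS. That model is multivariable, and the per-predictor rate is several-fold lower.

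**Ritual correlations are the least exposed.** They need a video of the patient's own ritual (section 3.3d), so they probably rest mainly on patients with compulsions. This stands. The issue bears most on SOFAS, BABS, basic symptoms, trauma, mood and personality.

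**A pooled, dimensional association can be a legitimate target.** Sections 2 and 7 speak of the obsessive-compulsive spectrum and its relation to schizophrenia-spectrum disorders. This is fair for those aims, and is a reason to report within-diagnosis estimates beside pooled ones rather than to ban pooling. It does not cover the insight aim, which section 2 places in OCD.

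**Comorbid patients.** A reader might infer from the eligibility wording that patients with both diagnoses are counted in both groups, so that a two-group test loses independence. No text says so. The groups are undefined, which is an ambiguity and not double counting.

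**Conclusion.** The point holds in a limited form. As written, the BABS regression does not match the OCD question it is meant to answer, and neither the correlations nor the two regressions account for diagnosis in a sample recruited across two diagnoses. Associations reported from them can be confounded by diagnosis or masked by it.

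The size cannot be fixed from the protocol. For one correlation under a 1:1 mix and n = 100, it runs from no material effect at d = 0.3 to a rejection rate of about one in two at d = 1 and nearly certain rejection at d = 1.5. An uneven mix reduces it, and so does entering many similarly shifted predictors together. The figures assume no within-diagnosis link and equal shifts on the variables involved.

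The documents do not show that such differences exist in this sample, that the ritual correlations are seriously affected, or that any patient is counted twice.

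**What to change.** Change section 4 as follows:

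- Fit the BABS regression in patients with OCD, with an indicator for a co-occurring schizophrenia-spectrum disorder.
- In the SOFAS regression, and in correlations that use both diagnoses, adjust for diagnosis in three categories (OCD only, schizophrenia spectrum only, both). For correlations this means partial correlations.
- Check the diagnosis-by-predictor interaction, since adjustment alone removes mean differences but assumes a common slope.
- Report within-diagnosis estimates beside any pooled estimate.
- Define the two groups in the simultaneity and training comparisons so that each comorbid patient is assigned once.

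Diagnosis is already established by the SCID-5-CV at entry, so no new data are needed. The cost is a few degrees of freedom (two for a three-category diagnosis term, more where interactions are fitted) and a smaller sample for the insight model.

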### **Study Design:**

Observational (medication-free), cross-sectional, multicenter

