#### *-Predisposing Factors for Loss of Insight*

Numerous studies in the literature report a high comorbidity between OCD and Personality Disorders (PD), with prevalence rates up to 20.8%. However, the role that premorbid personality traits may play in modulating OCD symptoms or influencing insight loss has been scarcely investigated.

Obsessive-Compulsive Personality Disorder (OCPD) has been inversely correlated with poor-insight OCD forms, suggesting a protective role, while Cluster A PDs (particularly Schizotypal

and Schizoid) and Cluster B PDs (Borderline and Narcissistic) have been more frequently associated with poor-insight forms.

There is also limited literature on comorbidity between poor-insight OCD forms and other Axis I Disorders. Some authors hypothesize a higher frequency of psychiatric disorders during childhood in patients with poor insight. Other studies have reported a higher prevalence of depressive disorders or greater severity of depressive symptoms in patients with poor-insight OCD, suggesting that affective state may influence insight level in the disorder.

Conversely, other authors found no correlation between obsessive and affective dimensions.

Therefore, this study aims to further explore the role of possible predisposing factors for insight loss, particularly affective or personality-related variables.

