#### *1.1c The Role of Trauma*

Childhood trauma is considered a common risk factor for several psychiatric disorders: Mood Disorders, Substance Use Disorders, Psychotic Disorders Eating Disorders, and Personality Disorders.

Studies have also indicated a link between various types of childhood trauma—especially emotional abuse and emotional neglect—and the development of OCS. A causal relationship between traumatic events and the onset of symptoms has also been hypothesized.

However, the mechanism by which childhood-adolescent trauma may predispose individuals to OCS development remains underexplored. A recent study by Bey et al. (2017) proposed a possible link between childhood trauma and specific temperamental traits: particularly, high levels of "harm avoidance" are considered a premorbid vulnerability factor and an endophenotype of OCD.

The objective of this study is to retrospectively explore the possible presence of childhood and adolescent trauma in OCD patients using dedicated scales and to assess whether such trauma may have a predisposing role in the onset of OCS or OCD spectrum disorders, or a pathoplastic role in shaping clinical manifestations.

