### 3.3b Self-Administered Questionnaires

- Leyton Obsessional Inventory (LOY) A 69-item scale assessing OCS in daily life aspects (e.g., recurring thoughts, fears, ordering and checking rituals, indecision) and obsessive personality traits (e.g., meticulousness, punctuality, rigidity). Each item requires a yes/no answer. For positive answers, resistance to symptoms (rated on a 5-point scale from 0 = none to 4 = maximum resistance) and interference with global functioning (rated on a 4-point scale from 0 = none to 3 = maximum interference) are assessed.
- Frankfurter Beschwerde Fragebogen (FBF) Questionnaire for assessing basic pre-psychotic symptoms, consisting of 98 true/false items grouped into 10 phenomenological dimensions: loss of control, simple perceptual disturbances, complex perceptual disturbances, receptive and expressive language disorders, thought disorders, memory disturbances, motor disturbances, loss of automatisms, anhedonia-anxiety, and sensory overload.
- Childhood Trauma Questionnaire (CTQ) A retrospective questionnaire investigating five types of traumatic experiences during childhood-adolescence: emotional abuse, emotional neglect, physical abuse, physical neglect, and sexual abuse. It includes 28 items (short version) or 34 items (standard version), rated on a scale from 1 (never) to 5 (very often). The short version has been standardized and validated in France and adapted to Italian through psychometric techniques.
- Temperament and Character Inventory (TCI) A 240-item self-assessment tool evaluating personality based on Cloninger's biosocial model. It includes 4 temperament and 3 character dimensions, each with corresponding subscales. Raw scores are transformed into standardized T scores and graphed to create a personality profile. Temperament dimensions include Harm Avoidance, Novelty Seeking, Reward Dependence, and Persistence.

- Adult Temperament Questionnaire - Short Form (ATQ-SF) Consists of 77 items rated on a 7-point Likert scale (1 = extremely false, 7 = extremely true), measuring:
  1. Effortful Control (attention control, inhibitory control, activation control);
  2. Orienting Sensitivity (perceptual, associative, and affective sensitivity);
  3. Extraversion (sociability and tendency to experience positive emotions);
  4. Negative Affect (tendency to experience negative emotions). A score  $\leq 67$  on the EC scale indicates low self-regulation capacity.

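### For symptom severity, basic symptoms, temperament and ritual form, trauma (CTQ) is analysed only by crude Pearson correlation, so an influence of current mood cannot be seen although HAM-D is collected

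*Protocol*

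**What the plan says.** Protocol section 1.1c sets the question: to explore retrospectively childhood trauma in OCD patients and "assess whether such trauma may have a predisposing role in the onset of OCS or OCD spectrum disorders, or a pathoplastic role" in the clinical picture. Section 3.3b measures trauma with the CTQ: "A retrospective questionnaire investigating five types of traumatic experiences during childhood-adolescence". The design is given as "Observational (medication-free), cross-sectional, multicenter".

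Section 4 fixes the analysis: "Pearson's correlation will be used to assess associations between formal characteristics of ritualized actions (J-Watcher scores), OCD symptom severity (Y-BOCS"), and the list continues with "childhood-adolescent trauma (CTQ), affectivity (HAM-D"), the basic-symptom scales, personality, temperament and SOFAS. HAM-D is one more member of this list, not a covariate.

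Two multivariable analyses follow. If correlations are significant, an Enter-method linear regression is run "using SOFAS total score as the dependent variable and demographic variables and questionnaire scores as independent variables". The same analysis is then applied with total BABS score as the outcome. HAM-D is not named in either, but section 3.3c lists it among the clinician-administered questionnaires, so it can be a predictor there together with CTQ. No such model is planned for Y-BOCS, FBF, SPI-A, temperament or J-Watcher scores.

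**The concern.** Symptom severity, basic symptoms and ritual form are among the manifestations that "a pathoplastic role in shaping clinical manifestations" would concern, and for them the plan yields only unadjusted coefficients. CTQ is a recalled self-report, collected in a cross-sectional study that also rates current depression. If patients who are low at assessment report more trauma and also score higher on the outcome, CTQ and outcome will correlate even if trauma has no effect. FBF, TCI and ATQ are themselves self-reports, so mood could colour both sides of those correlations.

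At stake is the interpretation. A reader shown only the crude coefficient cannot tell how far it depends on mood at the time of recall, although the variable needed to show this is already being collected.

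**Working it through.** The protocol gives no sample size, power or expected correlation for this analysis, so there is no figure of its own to reproduce. The check asks what a crude correlation would show if trauma had no effect.

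**Inputs**
- Method: pairwise Pearson correlation, no covariate (section 4).
- Assumed: correlation of mood with CTQ, *a*, and with the outcome, *b*, each 0.2 to 0.5, plus one case with *b* = 0.
- Assumed: n = 50, 100 or 200.
- Assumed: two-sided 5% level. The only p-value threshold in section 4 concerns the fit of the simultaneity model.

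**Step 1: expected crude correlation.** If mood drives both variables and there is no other link, r = a × b.

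**Step 2: chance of significance.** By Fisher's z, with δ = atanh(r) × √(n − 3), the probability is 1 − Φ(1.96 − δ) + Φ(−1.96 − δ). Example with 0.4 × 0.4 and n = 100: r = 0.16, atanh(r) = 0.1614, √97 = 9.849, δ = 1.59, probability 35.6%.

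| a × b | crude r | n = 50 | n = 100 | n = 200 |
|---|---|---|---|---|
| 0.2 × 0.2 | 0.04 | 5.9% | 6.8% | 8.7% |
| 0.3 × 0.3 | 0.09 | 9.5% | 14.4% | 24.5% |
| 0.3 × 0.5 | 0.15 | 17.9% | 31.9% | 56.4% |
| 0.4 × 0.4 | 0.16 | 19.8% | 35.6% | 62.0% |
| 0.5 × 0.5 | 0.25 | 41.7% | 71.1% | 94.8% |
| 0.4 × 0 | 0 | 5.0% | 5.0% | 5.0% |

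A simulation with 4,000 replicates per cell agrees. At n = 100, for example, it gave 7.0%, 13.8% and 72.0% for the 0.2, 0.3 and 0.5 pairs.

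**Step 3: after partialling out mood.** The partial correlation is (r − ab) / √[(1 − a²)(1 − b²)], which is 0 when r = ab. In the simulation it was significant in 4.3% to 5.5% of replicates in every cell, against a nominal 5%. This assumes that HAM-D measures mood without error.

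**Step 4: what the partial correlation cannot settle.**
- *Mediation.* If trauma raises depression and depression raises symptoms (0.4 and 0.4, no direct path), the crude r is again 0.16 and the partial is 0. This is the same pattern as confounding.
- *Common effect.* If trauma and symptoms each raise HAM-D (0.4 and 0.4) and are otherwise unrelated, the crude r is 0 and the partial is (0 − 0.16) / (1 − 0.16) = −0.19, an artefact of adjustment.
- *Overlap.* By section 3.3c the 21-item HAM-D includes an obsessive-compulsive item, so partialling it out of a Y-BOCS correlation removes part of the outcome.

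**The case against.** The strongest reply is that the trauma question tied most closely to mood already has a multivariable analysis. Section 2 lists trauma and affective factors together as possible contributors to loss of insight, and the BABS regression can hold CTQ and HAM-D at once, as can the SOFAS regression. This stands. A reader might infer that the whole role of trauma is judged from crude correlations; the protocol does not support that. The point is confined to the outcomes without a regression.

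A reader might also infer that the protocol itself treats mood as shaping the clinical picture in general. It does not. The relevant remark, "suggesting that affective state may influence insight level in the disorder", reports what other studies suggest and concerns insight only. The same subsection also cites authors who found no correlation between obsessive and affective dimensions.

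Nor does any section say that mood colours CTQ recall or that CTQ and HAM-D are taken in one session; the design is only called cross-sectional. Section 3.1 provides for informing patients and seeking consent only once their condition is stable, which may narrow the range of mood but does not remove it. Ritual form is coded from video with software, and there is no stated reason why low mood should raise those scores. For that outcome the mechanism is the least plausible.

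Finally, section 4 speaks of associations, section 1.1c is exploratory, and an unseen SAP could add adjustment. All true. But for these outcomes the protocol names its method, and section 1.1c asks about a predisposing or pathoplastic role, which an unadjusted coefficient alone cannot address.

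**Conclusion.** The point holds in a limited form. For CTQ against Y-BOCS, FBF, SPI-A, temperament and, less plausibly, J-Watcher scores, the plan offers only crude correlations, and these can reflect current mood rather than trauma. The size cannot be taken from the documents. Under the assumed mood correlations it runs from negligible (r = 0.04, about 7% significant at n = 100) to serious (r = 0.25, about 71%), and it is nil where mood is unrelated to the outcome.

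Two stronger readings are not supported. One is that the planned correlations are in fact biased: the documents show only that they could be. The other is that a link which vanishes on adjustment is refuted, or that the crude and adjusted values bracket the truth. Mediation gives the same pattern as confounding, and a common-effect structure can push the adjusted value to −0.19 when there is no link at all.

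**What to change.** Add to section 4: for each correlation of CTQ with Y-BOCS, FBF, SPI-A, temperament and J-Watcher scores, report the crude coefficient and, as a sensitivity analysis, the partial correlation given HAM-D, both with 95% intervals. When the outcome is Y-BOCS, compute HAM-D without its obsessive-compulsive item.

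State the reading in advance. The two values are not bounds, and the adjusted value is not a pass/fail test. Where they differ materially, say that the association cannot be separated from current mood, which may be a confounder or a mediator, and describe it as an association only.

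The cost is a few sentences and one extra table column; no new data are needed. The drawback is that the adjusted value may understate a trauma effect that acts through depression, which is why the crude value stays beside it.

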### *1.3 Multisensory Integration*

Multisensory integration refers to the ability to combine stimuli from different sensory modalities, offering both behavioral and perceptual benefits to the individual. Among various integrative modalities, the one with the highest resolution is auditory-tactile (AT), which is superior to audiovisual (AV) and visuotactile (VT) integration.

The key element in this process is the "temporal proximity" of stimuli, meaning their arrival within a specific time window. In nature, stimuli coming from the same source are perceived as nearly simultaneous. At the neural level, multisensory cells show increased activity when receiving different types of stimuli within a certain "temporal window," allowing for improved performance compared to when they receive unisensory stimuli.

These integrative areas remain plastic for much of the individual's life, allowing neural representations to closely match the spatial-temporal features of the subject's environment. As early as two months of age, humans show the ability to perceive multisensory asynchronies, and through childhood, adolescence, and adulthood, a process of plastic remodeling of these circuits occurs, based on the subject's experiences.

---

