## **6. Safety Concerns**

No anticipated risks, physical or psychological consequences are expected from this study, which will not interfere with standard clinical care. Patients will continue to be monitored and treated by their usual clinical providers.

During questionnaire completion, some participants may temporarily experience sadness, discouragement, or irritation when recalling unpleasant past experiences. However, any such emotions are unlikely to last beyond the duration of the session. Patients may discuss their concerns at any time with a study physician.

Thus, study-related risks are not greater than those encountered in daily life. Participation is voluntary and can be withdrawn at any time. Any damages (attributable to AUSL Parma or its

personnel during the study) are covered under the Regional Risk Management Program for public health entities.

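### The simultaneity-range comparison between non-randomised diagnostic groups names no covariates, although age and sex are collected and the same section uses demographic variables elsewhere

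*Protocol*

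**What the plan says.** Protocol section 4 (Statistical Analysis) derives an SR for each participant from the Independent Channels Model and then states: "SR values from both experimental groups will then be compared and correlated with psychopathological scales using standard parametric" tests, with non-parametric tests if the data are not normal. Pre- and post-training medians are likewise compared between the groups and related to the scales. Rubber Hand data are analysed against psychopathological variables with the same kind of tests. No covariate, matching or stratification is named for any of these.

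Earlier in the same section, the regressions for SOFAS and BABS take "demographic variables and questionnaire scores as independent variables". SR is not a dependent variable there.

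The relevant data are collected. Section 3.3a says "Participants will complete a questionnaire including age, sex, years of education", and adds from interview and records "diagnosis at onset, initial treatment, family history, age at onset, and current therapy". Section 3.2a admits patients aged 18 to 65 with either diagnosis or both. Section 1.3 says of multisensory circuits that across the lifespan "a process of plastic remodeling of these circuits occurs".

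On treatment, the design line reads "Observational (medication-free), cross-sectional, multicenter", while section 6 says "Patients will continue to be monitored and treated by their usual clinical providers".

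**The concern.** The groups are formed by diagnosis, so they may differ in age and sex for reasons unrelated to multisensory integration. A plain group test on SR then mixes any diagnosis effect with the effect of those differences. Correlations of SR or Rubber Hand ratings with symptom scales are open to the same distortion if age is related to both.

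This matters because section 2 wants to consider a deficit in integration as possibly central to the disorder. A difference that partly reflects age would be read in that light. The protocol's own SOFAS and BABS regressions show that multivariable analysis was written down where it was intended.

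**Working it through.** There is no planned figure to reproduce: section 3.1 refers to earlier studies for the sample size but gives no N, effect size, SD, power or alpha for the SR comparison. The check is therefore an illustration with assumed inputs.

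**Inputs, all assumptions:** r, the within-group correlation of age with SR; d, the difference in mean age between groups in SD units; n per group; no true diagnosis effect; two-sided 5% test.

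**Formulas:**
- Spurious SR difference in SD units: b = r × d.
- False-positive rate of the plain two-group test: P(|Z + b × √(n/2)| > 1.96), with Z standard normal.

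**Worked example:** r = 0.3, d = 1.0, n = 50. Then b = 0.30 and the shift is 0.30 × √25 = 1.50. The rate is P(Z > 0.46) + P(Z < −3.46) ≈ 0.323.

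| r | d | b | n = 30 | n = 50 |
|---|---|---|---|---|
| 0.2 | 0.3 | 0.06 | 5.6% | 6.0% |
| 0.3 | 0.5 | 0.15 | 8.9% | 11.7% |
| 0.3 | 0.7 | 0.21 | 12.9% | 18.3% |
| 0.3 | 1.0 | 0.30 | 21.3% | 32.3% |

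**Effect of sample size:** b does not contain n, so the bias stays while the standard error shrinks. At r = 0.2, d = 0.3 the rate goes from 5.4% (n = 20) to 7.1% (n = 100). At r = 0.3, d = 0.5 it goes from 8.9% (n = 30) to 18.6% (n = 100).

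**Check by simulation (4,000 runs per setting):** at r = 0.3, d = 0.5, n = 50 the plain t-test rejected in 11.2% of runs, against 11.7% by formula. With the covariate in a linear model, the rate was 4.4% to 5.5% in all nine settings tried: n = 30, 50 or 100, crossed with (r, d) = (0.3, 0.5), (0.5, 0.5) and (0.5, 0.8). This assumes that the covariate acts linearly and is measured without error.

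**The case against.** Covariate choice is often left to a statistical analysis plan, and one may exist here. A reader might infer that the protocol rules adjustment out. It does not: it never uses the words unadjusted or two-sample, and analysis of covariance is also a standard parametric method. What stands is that the protocol describes a method for SR and names no covariate, while naming demographic variables for two other outcomes in the same section.

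A reader might also infer that age and medication do differ by diagnosis, or that medication must add to an age effect. The documents give no distribution of either by group, and a medication effect could as well offset an age effect. Section 1.3 describes lifelong, experience-based plasticity; it does not state an age trend in SR among adults of 18 to 65. At the benign end of the assumed range the harm is negligible.

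Finally, the study is observational, and section 2 speaks of correlations and of what may be the case. A group difference is a legitimate descriptive result. Nor would adjustment make it attributable to diagnosis: drug class may nearly coincide with diagnosis. Education may be partly a consequence of illness, since section 1.2 places schizophrenia onset in late adolescence or the twenties, with cognitive deficits. These points limit what the fix can claim and which covariates belong in the main model. They do not argue against adjusting for age and sex.

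**Conclusion.** The point holds as a recommended improvement. SR and training medians are to be compared between non-randomised groups, with no matching stated and no covariates named, although age and sex are already collected. The bias exists only if age (or sex) is both related to SR and unevenly distributed between groups. Its size cannot be known from the documents: the 5–7% to 32% range rests wholly on assumed r, d and n.

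The stronger reading, that a group difference will in fact be due to age or medication, is not supported. The supportable statement is that the plan as written could not distinguish these explanations, and that an age- and sex-adjusted model removes part of the ambiguity at little cost.

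The medication-free label is a separate matter of wording. Taken literally it conflicts with recording current therapy (section 3.3a) and with continued usual treatment (section 6). It may only mean that the study gives no drug, and it does not strengthen the confounding argument.

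**What to change.** 1. Define the two experimental groups in section 4, and say how a patient with both diagnoses, admitted by section 3.2a, is classified. No adjusted model can be specified until this is done.
2. Make the primary SR comparison a linear model with diagnosis, age and sex, on the log scale or rank-based if SR is skewed. Show the unadjusted result beside it.
3. Use age- and sex-adjusted partial correlations or regressions to relate SR, training change and Rubber Hand ratings to the scales, and include age and sex when training change is compared between groups.
4. Add years of education and current therapy only as sensitivity models. Report the overlap of drug classes between groups, so that the reader can see whether therapy and diagnosis can be separated at all.
5. Describe all group differences as associations.
6. Reconcile the design line with sections 3.3a and 6 by stating what medication-free means.

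The cost is wording, a little more analysis and a small loss of degrees of freedom: two, for age and sex entered as single terms. No new data are needed. Where a drug class nearly coincides with a diagnosis, the therapy model will give wide intervals, which is why it is not the primary analysis.
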